4. PLANNED ANALYSIS

4.1. Interim Analysis

No interim analysis was planned and hence no multiplicity adjustment for interim analysis is needed.

4.2. Final Analysis

This SAP for 16 week will be finalized before database lock in week 16. The efficacy analysis performed at week 16 is the final efficacy analysis. The analysis for week 16 will be conducted using database up to 16 week after database lock in week 24.

4.3. Independent Data Monitoring Board

An independent data monitoring board will periodically assess unblinded data, and will make recommendations to the study sponsor regarding the appropriateness of continuing the study and about the need for protocol amendments.

The independent data monitoring board will include independent statistical and medical experts. For more details, the overseas independent data monitoring committee procedures (DMC Charter) will be followed.

5. ANALYSIS POPULATIONS

The analysis of efficacy will be performed in the full analysis set (FAS). The principal

analysis set for efficacy will be the modified FAS (mFAS). Secondary analyses of the primary efficacy endpoint and key secondary efficacy endpoint will also be performed in the per-protocol set (PPS). The analysis of safety will be performed in the safety analysis set (SAF). The analysis of pharmacokinetics will be performed in the pharmacokinetic analysis set.

The analysis sets are defined below. For the contents of the data review meeting, refer to a separate materials.

(1) Efficacy analysis sets

1) Randomized subjects (RAND)

2) FAS

The FAS will consist of all randomized subjects except for the following subjects.

- Subjects who have not received study drug even once
- Subjects with no WOMAC pain subscale score (the primary endpoint) at baseline
- Subjects with no WOMAC pain subscale score (the primary endpoint) at any time point after randomization

3) Modified FAS (mFAS)

The mFAS will consist of the FAS, except for the following subjects.

- Subjects who are randomized to 3 mg q4w group
- Subjects who are randomized to 6 mg q8w group

4) PPS (This set will be used for only statistical analysis for the data obtained from screening to Week 16)

The PPS will consist of the mFAS, except for the following subjects.

- Subjects who did not meet the inclusion criteria
- Subjects who met the exclusion criteria
- Subjects who did not comply with the rules on prohibited concomitant drugs/therapies
- Subjects who did not complete the period from study treatment initiation through the assessment of the WOMAC pain subscale score (the primary endpoint) at Week 16
- Subjects who did not receive four injections of study drug

(2) SAF

The SAF will consist of all randomized subjects except for the following subjects

- Subjects who did not receive study drug even once
- Subjects for whom absolutely no post-randomization safety data are available

6. STATISTICAL CONSIDERATIONS

6.1. Descriptive Statistics

(1) Non-PK related

Continuous data will be summarized descriptively using the number in the analysis set (N), the number of observations (n), mean, standard deviation (SD), median, minimum and maximum. Categorical data will be summarized using frequency counts and percentages. The denominator for the percentages will be the total number of subjects in the treatment group and analysis population being presented, unless otherwise specified.

6.2. Statistical Tests

Unless otherwise specified, all formal statistical tests of treatment effects will be done at two-sided significance level of 0.05. Point estimates will be accompanied with two-sided 95% CIs where applicable.

7. DATA CONVENTIONS

7.1. Analysis Variable Definitions

7.1.1. Study Subjects

7.1.1.1. Demographic and Other Baseline Characteristics

(1) BMI

BMI will be recalculated using the formula below and reported to 1dp.

BMI (kg/m^2) = weight at screening (kg) / {height at screening (m)}²

(2) Age(years)

If (month of date of consent > month of date of birth) or (month of date of consent = month of date of birth and day of date of consent \geq day of date of birth), then Age (years) = year of date of consent - year of date of birth

if else case, then Age (years) = year of date of consent - year of date of birth - 1.

(3) Time since osteoarthritis diagnosis (years)

If (month of date of consent > month of osteoarthritis diagnosis) or (month of date of consent = month of date osteoarthritis diagnosis, and day of date of consent \geq day of date of osteoarthritis diagnosis), then Time since osteoarthritis diagnosis (years) = year of date of consent - year of date of osteoarthritis diagnosis

if else case, then Time since osteoarthritis diagnosis (years) = year of date of consent - year of date osteoarthritis diagnosis - 1.

Impute date of osteoarthritis diagnosis as the earliest possible date (i.e. first day of month if day is unknown or 1st January if day and month are unknown).

7.1.1.2. Treatment Duration and Compliance

(1) Treatment Duration

- 1) Treatment Duration (days) = The date of last study drug injection prior to week 16 - the date of the first study drug injection + min(28 or (the date of last study drug infection - the date of Week 16 study drug injection))
- 2) Criteria for pre-defined limit

Treatment duration period ≥ 1 day, ≥ 29 days, ≥ 57 days, ≥ 85 days, and ≥ 113 days

(2) Treatment Compliance

- 1) Treatment compliance will be calculated using the formula below and reported to 1dp.
Treatment compliance(%) = (Number of injections of study drug during treatment exposure period) / (Number of planned injections of study drug during exposure period on or before the time that the subject discontinues from the study) x 100%

2) Criteria for pre-defined limit

the number of injections of study drug: 1, 2, 3 and 4

7.1.2. Efficacy assessments

7.1.2.1. WOMAC pain subscale score

WOMAC pain subscale score

$$= \frac{\text{sum of items from Section A 1 to Section A5 in questionnaire}}{5}$$

7.1.2.2. WOMAC physical function subscale score

WOMAC physical function subscale score

$$= \frac{\text{sum of items from Section C 8 to Section C24 in questionnaire}}{17}$$

7.1.2.3. WOMAC stiffness subscale score

$$\text{WOMAC stiffness subscale score} = \frac{\text{Section B 6 + Section B7 in questionnaire}}{2}$$

7.1.2.4. WOMAC total score

WOMAC total score

$$= \frac{\text{sum of items from Section A1 to Section C24 in questionnaire}}{24}$$

7.1.2.5. NRS score

- Weekly average walking index joint pain

Baseline is defined as the average of the non-missing values during 7 days prior to taking study drug. For each week, the average of the non-missing values during the 7 days on or prior to that week will be used.

- Daily walking index joint pain

Baseline is defined as the last non-missing values prior to taking study drug.

7.1.2.6. SF-36 / EQ-5D-5L

- SF-36

Physical, Mental and Role social component summary will be calculated considering factor coefficients based on the 1995 Japan National Survey. The derivation of 8 subscales and three component is detailed in appendix 13.1.

- EQ-5D-5L

Utility Index Score will be calculated using the formula and Table below.^[1]

Utility Index Score

= 1 + [Estimation of the constant term(if all answer is not 1)]

+ [Sum of "estimation of coefficients corresponding to answer other than 1"]

[figure not shown]
Item	Level	Estimation	Standard Error	P-value
Mo	Intercept	-0.060924	0.013625	<0.0001
	2	-0.063865	0.008996	<0.0001
	3	-0.112618	0.009287	<0.0001
	4	-0.179043	0.010231	<0.0001
	5	-0.242916	0.009425	<0.0001
Sc	2	-0.043632	0.008931	<0.0001
	3	-0.076660	0.009972	<0.0001
	4	-0.124265	0.010129	<0.0001
	5	-0.159659	0.008924	<0.0001
	2	-0.050407	0.009205	<0.0001
Ua	3	-0.091131	0.010005	<0.0001
	4	-0.147929	0.009744	<0.0001
	5	-0.174786	0.009115	<0.0001
	2	-0.044545	0.008354	<0.0001
	3	-0.068178	0.010052	<0.0001
Pd	4	-0.131436	0.008985	<0.0001
	5	-0.191203	0.009604	<0.0001
	2	-0.071779	0.009701	<0.0001
	3	-0.110496	0.010863	<0.0001
	4	-0.168171	0.009850	<0.0001
Ad	5	-0.195961	0.009164	<0.0001

Mo: mobility, Sc: self-care, Ua: usual activities,

Pd: pain/discomfort, Ad: anxiety/depression

e.g) If answer is [1 1 1 1 1], Utility Index Score is = $1 + 0 + 0 = 1$. If answer is [1 1 3 2 1], Utility Index Score is = $1 + (-0.060924) + (-0.091131 - 0.068178) = 0.779767$.

7.1.2.7. Response rate based on the OMERACT-OARSI criteria

Note that the criteria in the diagram above are based on standardized score between 0 and 100. For this study, WOMAC pain and physical function subscale score are between 0 and 10, so the absolute change required for response is the required change in the diagram above divided by 10; PGA is 1, 2, 3, 4 or 5, so the absolute change required for response is at least 1 point.

7.1.2.8. Rescue Medication

Baseline amount of rescue medication use is defined as the average of the non-missing values during 7 days prior to taking study drug. For each week, the average of the non-missing values during the 7 days on or prior to that week will be used.

7.1.3. Safety Assessments

The on-treatment period is defined as the time from first dose of investigational product up to 28 days after the last dose of investigational product excluding adverse events after study drug sc administration at week 16.

7.1.3.1. Adverse Events

Adverse events will be coded according to the MedDRA version 20.1

(1) Treatment Emergent Adverse Events/ Treatment Emergent Serious Adverse Events (TEAEs/TSAEs)

An AE/SAE is classified as treatment emergent if it newly occurred after the first dose of study drug or if a pre-dose event increases in severity following the first dose of study drug.

(2) Adverse Drug Reaction

A TEAE is considered “adverse drug reaction” if it has been assessed as having a “reasonable

possibility" in relationship to the study drug.

(3) Adverse Event of Special Interest(AESI)

Adjudicated arthropathy, sympathetic nerve disorders and altered peripheral sensation are defined as adverse events of special interest (AESI) to facilitate characterizing the safety profile of MT-5547.

(4) Duration of Adverse Events

Duration of Adverse Events (days) = AE stop date – AE start date + 1

7.2. Analysis Visit Definitions

(1) General analysis visit definitions

Analysis visit	Nominal day	Window
Baseline	Day 1	<Day 1
Week 1	Day 8	Day 2 to 11
Week 2	Day 15	Day 12 to 21
Week 4	Day 29	Day 22 to 43
Week 8	Day 57	Day 44 to 71
Week 12	Day 85	Day 72 to 99
Week 16	Day 113	Day 100 to 127

(2) For NRS analysis visit definitions

Analysis visit	Window
Baseline	Day -7 to -1
Week 1	Day 1 to 7
Week 2	Day 8 to 14
Week 3	Day 15 to 21
Week 4	Day 22 to 28
Week 5	Day 29 to 35
Week 6	Day 36 to 42
Week 7	Day 43 to 49
Week 8	Day 50 to 56
Week 9	Day 57 to 63
Week 10	Day 64 to 70
Week 11	Day 71 to 77
Week 12	Day 78 to 84
Week 13	Day 85 to 91
Week 14	Day 92 to 98
Week 15	Day 99 to 105
Week 16	Day 106 to 112

The date of the first dose of study drug is defined as Day 1.

Unless otherwise specified, baseline will be the last observed value of the parameter of

interest prior to the first intake of study drug (this includes unscheduled visits). For other visits, if there are multiple data in a window, the closest data to nominal day will be used. If the distance to the nominal day is the same, the data of later date will be used.

7.3. Data Handling Convention for Missing Data

(1) Non-PK related

Efficacy:

WOMAC

WOMAC scores will be computed when one pain, one stiffness, or 1-3 physical function items are missing. The missing items will be imputed by the mean of available items within the same subscale. The scores will be set to missing if more items are missing.

NRS

If all values are missing for the 7 days, the value for that week is set to missing.

SF-36 / EQ-5D-5L

- SF-36 subscale scores will be computed if at least 50% of items are available. The missing items will be imputed by the mean of available items.
- EQ-5D-5L index will be set to missing if any of the 5 dimensions is missing.

Adverse events:

If severity or relationship is found to be missing the most severe occurrence will be imputed for the summary of interest.

For AE start missing or partial dates, the AE will be treated as TEAE if it cannot be determined to be a non-TEAE.

8. STATISTICAL METHODOLOGY

8.1. Study Subjects

8.1.1. Subject Disposition

Subject disposition will be summarized by treatment group, combined MT-5547 and overall on the randomized population.

8.1.2. Analysis Populations

Analysis populations will be summarized by treatment group, combined MT-5547 and overall on the randomized population.

8.1.3. Demographic and Other Baseline Characteristics

The following demographic and other baseline characteristics will be used.

	category	Descriptive
Sex	Male, Female	
Age(years)	<65, >=65	Yes
Height(cm)		Yes
Weight(kg)		Yes
BMI(kg/m2)	<25, >= 25 and < 30, >=30	Yes
Race	Japanese, other	
Time since OA diagnosis (years)	<1, >=1 and <5, >=5 and <10, >=10	Yes
Index Joint	Knee, Hip	
K-L score for index joint	1, 2, 3, 4	
WOMAC pain subscale score	<6, >=6	Yes
WOMAC Physical function subscale score	<6, >=6	Yes
PGA	1, 2, 3, 4, 5	Yes
Pain site	Right Knee, Left Knee, Right Hip, Left Hip, Right Shoulder, Left Shoulder	
Pretreatment drug	NSAIDs(Systemic use), NSAIDs(Topical use), Acetaminophen, Opioid, Monoamine reuptake inhibitor, Hyaluronic acid, Pregabalin, Herbal medicine, Other	
NSAIDs Inadequate Pain Relief	Yes, No	
NSAIDs Intolerance	Yes, No	
Ever taken Opioid for Pain due to OA	Yes, No	
Opioid Inadequate Pain Relief	Yes, No	
Opioid Intolerance	Yes, No	
Ever taken Acetaminophen for Pain due to OA	Yes, No	
Acetaminophen	Yes, No	

Inadequate Pain Relief		
Acetaminophen Intolerance	Yes, No	
NSAID + Opioid + Acetaminophen Inadequate Pain Relief	Yes, No	

Demographic and other baseline characteristics will be summarized by treatment group, combined MT-5547 and overall on the FAS population, PPS population and the SAF population.

Demographic and other baseline characteristics before the protocol amendment and after the protocol amendment will be summarized by treatment group, combined MT-5547 and overall on the mFAS population.

8.1.4. Treatment Duration and Compliance

Treatment duration will be summarized by treatment group and combined MT-5547 on the SAF population. Treatment compliance will be summarized by treatment group and combined MT-5547 on the SAF population.

8.2. Efficacy Assessments

Efficacy assessment will be summarized by treatment group on the mFAS population.

8.2.1. Primary Efficacy Endpoint

The change in the WOMAC pain subscale score from baseline to Week 16 will be summarized and plotted by treatment group.

Primary analysis method

The primary analysis will be tested using the estimator of mixed effect model for repeated measurement (MMRM) approach. The model will include the treatment group, measurement time point, treatment group and measurement time point interaction, stratification factor K-L grade (2-3 or 4), and stratification factor evaluated joint (knee or hip) as factors, and the baseline and baseline and measurement time point interaction as covariates. The within-subject correlation structure will be unstructured, and the denominator degrees of freedom for the test statistics of estimated parameters will be approximated using the Kenward-Roger method. In case the model will not converge with the unstructured covariance structure, Heterogeneous Autoregressive (1) (ARH[1]), Heterogeneous Compound Symmetry (CSH), Autoregressive (1) (AR[1]) or Compound Symmetry(CS) covariance structure will be used instead in this order.

- Evaluation on 1 mg q4w group

[figure not shown]
With pooling the data on 1 mg q4w and placebo obtained before and after the protocol amendment (Ver. 04.00.00000), the least square mean, standard error, P value, and 95% confidence interval of the difference between each of the MT-5547 1 mg q4w and the placebo group in the change in the WOMAC pain subscale score from baseline to Week 16 will be calculated using the MMRM approach.

- Evaluation on 1 mg q8w group

Using only the data obtained after the protocol amendment (Ver. 04.00.00000), the least square mean, standard error, P value, and 95% confidence interval of the difference between each of the MT-5547 1 mg q4w, MT-5547 1 mg q8w and the placebo groups in the change in the WOMAC pain subscale score from baseline to Week 16 will be calculated using the MMRM approach.

MMRM that assumes that the missing mechanism is missing at random (MAR) is an analysis method in which missing values are not replaced. This model will be used to estimate the treatment effect in the mFAS when subjects continue receiving treatment through Week 16.

The SAS code planned for the analysis is outlined below.

Sensitivity analyses

Sensitivity analysis will use the same estimator as for the primary analysis. Likelihood based model method on the mFAS under Missing Not at Random(MNAR) assumption will be performed using the same MMRM as specified for the primary analysis. The following additional analyses will be performed for the primary efficacy endpoint.

- **Multiple Imputation (MI) analysis by Reason for Discontinued Treatment**

The missing data for patients who discontinued treatment due to lack of efficacy or AEs will be imputed with values centered at the mean baseline value of the treatment group that patients were randomized to. The missing data for patients discontinued treatment due to other reasons will be imputed under missing-at-random assumption using the regression method with adjustment for covariates including treatment group, randomization strata, and baseline score. Intermittently missing data will be imputed using Markov Chain Monte Carlo method.

The primary efficacy variables will be analyzed using a multiple imputation approach with mixed-effect model for repeated measure (MMRM) based on the mFAS with adjustment for missing data due to treatment discontinuation for the reasons of lack of efficacy or AEs assuming the WOMAC scores would on average return to baseline values. Missing data up to week 16 will be imputed 50 times to generate 50 complete data sets by using the SAS procedure PROC MI following the 4 steps below:

Step 1: This methodology will structure data based on missing data patterns. The Pattern Mixture Model (PMM) method will be based on a missingness pattern having a monotone structure, i.e. if among the observations over time one data value is missing, all other values after this missing value will also be missing. For patients with intermittent missing values, before performing MI based on the PMM, it will be necessary to create a monotone missingness pattern. Intermittent missing values will be imputed using the Markov Chain Monte Carlo (MCMC) methodology which assumes a multivariate normal distribution over all variables included in the imputation model. The MI procedure in SAS will be used for this purpose and this first MI step is planned to be repeated 50 times, creating different datasets with a monotone missing data structure. Seed value of 1995 will be used in the MI procedure. The imputation is based on the MAR assumption, i.e. the missing data are assumed to follow the same model as the other patients in their respective treatment group.

The following SAS code will be used to generate the monotone missing data pattern:

[REDACTED]

[REDACTED]

[REDACTED]

Step 2: After this, the remaining missing data will be imputed using a method for monotone missingness, also based on the MAR assumption. Thus, for each of the created dataset with a monotone missing data pattern, the MI procedure in SAS will be used to impute missing values within the instrument range based on a sequential procedure reflecting the monotone missing data pattern. Patients with the first missing value occurring at Week 1 ('W1') will have their missing Week 1 value replaced by an imputed value from a regression model with treatment group ('TRTP'), K-L grade ('GRADE') , index joint ('INDEX') and baseline ('BASE') value as explanatory variables. In the next step, patients with their Week 2 ('W2') value missing will have their missing Week 2 value replaced by an imputed value from a regression model with treatment group, grade, index and baseline and the Week 1 value as explanatory variables. Similar procedure will be used to replace the missing values at Week 4, Week 8, Week 12 and Week 16.

The following SAS code will be used to make the imputation with the MAR assumption:

[REDACTED]

[REDACTED]

[REDACTED]

[REDACTED]

[REDACTED]

Step 3: The initially missing and now imputed data for patients discontinued from the study treatment due to lack of efficacy or AEs will be adjusted to be centered at the mean baseline value for that treatment group, i.e., final imputed score = imputed score under MAR - (mean change from baseline score at the post-baseline time point* for the treatment group based on patients on treatment with non-missing data at that time point).

* MMRM models similar to that described for the primary analysis will be run on each of the 50 generated imputed datasets and the differences between the treatment groups at the

post-baseline time point.

Step 4: The imputed datasets generated with the approach described above do contain only non-missing values and are used as input in the model for the sensitive analysis for the primary efficacy endpoint. Any score imputed outside the range of the WOMAC subscale score of 0-10 will be truncated to the nearest permissible value on the WOMAC scale. MMRM models similar to that described for the primary analysis will thus be run on each of the 50 generated imputed datasets and the differences between the treatment groups at Week 16 of the DBDD Maintenance period will be estimated (and export to data 'ESTIMATES'). Finally, the MIANALYZE procedure in SAS will be applied to combine the results from these analyses to derive an overall estimate of the treatment differences at W16 according to the following code. In addition to the estimates, corresponding 95% confidence intervals and p-values will be calculated.

[REDACTED]

[REDACTED]

[REDACTED]

● **Tipping Point Analysis with MNAR assumption**

Sensitivity analysis using a tipping point approach with multiple imputation will be performed to assess the robustness of the results due to data that may be missing not-at-random (MNAR).

This approach will introduce a sensitivity parameter, δ . Estimations will be performed using multiple imputation methodology. Missing data up to week 16 time point will be imputed 50 times to generate 50 complete datasets by using SAS procedure PROC MI for each δ following the 3 steps below:

Step 1 and 2: The same as step 1 and 2 for Multiple Imputation (MI) analysis by Reason for Discontinued Treatment. The imputation is based on the MNAR assumption, not based on the MAR assumption. Any score imputed outside the range of the WOMAC subscale score of 0-10 will be truncated to the nearest permissible value on the WOMAC scale.

The following SAS code will be used to make the imputation with the MNAR assumption:

[REDACTED]

[REDACTED]

[REDACTED]

Step 3: Each imputed data set will be analyzed using the MMRM model with treatment, randomization strata, and relevant baseline included in the model. For each δ the SAS MIANALYZE procedure will be used to generate valid statistical inferences by combining results from the 50 analyses using Rubin's formula. By progressively increasing δ , the sensitivity analysis will explore the tipping points, e.g., δ value when the p-value for a treatment comparison is above 0.05. Results will be then summarized using summary tables and graphs.

[REDACTED]

Multiplicity adjustment

Because this study is a confirmatory study, in order to keep the family wise type 1 error rate to a significance level of 5% (alpha), two-sided, in the tests of the following hypotheses regarding the primary endpoint and the key secondary efficacy endpoint, a gatekeeping method based on a graphical approach will be used to perform multiplicity adjustment, as shown in Figure 8.2.1-1 to verify the hypotheses (Bretz et al., 2009). This multiplicity adjustment will only be performed for the statistical analyses of data from the double-blind period from screening to Week 16 after treatment initiation.

- Null hypothesis H01: The change from baseline in the WOMAC pain subscale score at Week 16 in the 1 mg SC q4w group is the same as that in the placebo group
- Null hypothesis H02: The change from baseline in the WOMAC pain subscale score at

Week 16 in the 1 mg SC q8w group is the same as that in the placebo group

- Null hypothesis H03: The change from baseline in the WOMAC physical function subscale score at Week 16 in the 1 mg SC q4w group is the same as that in the placebo group
- Null hypothesis H04: The change from baseline in the WOMAC physical function subscale score at Week 16 in the 1 mg SC q8w group is the same as that in the placebo group

[figure not shown]

Figure 8.2.1-1: MT-5547 Multiple Test Procedure

Subgroup analysis

Subgroup analyses will be performed on the primary endpoint. Each subgroup is following at baseline timepoint:

- index joint (hip or knee)
- K-L score category(2-3 or 4)
- WOMAC pain (<6 or ≥ 6)
- OA Duration(<5 or ≥ 5)
- age (<65 or ≥ 65)
- sex(Male, Female)
- BMI (<25 or ≥ 25)
- Weight(<median or \geq median)
- Opioid (Yes or No)

Each subgroup will be analyzed separately for the primary endpoint using MMRM model similar to the primary model.

Change from baseline to week 16 for the subgroup of index joint (hip or knee) and K-L score category(2-3 or 4) will be summarized by visit. Change from baseline to week 16 for the other subgroup will be summarized at week 16. In addition, forest plot depicting the treatment effect, p-values for interaction terms between the treatment group and each subgroup and 95% CI for each subgroup will be displayed.

Supplemental analysis

The PPS will be analyzed using the same method as for the primary analysis to confirm the robustness of the results of the primary analysis for the effects of the analysis set.

Supplementary analysis with respect to the data pooling on 1 mg q4w and placebo

The data on 1 mg q4w and placebo obtained before and after the protocol amendment (Ver. 04.00.00000) will be analyzed using the same method as for the primary analysis to confirm the data homogeneity and the robustness of the results of the primary analysis. Also, homogeneity in demographic and other baseline characteristics [Section 8.1.3] between data obtained before and after the protocol amendment will be confirmed.

Supplementary analysis with respect to response the site differences

Absolute values and changes from baseline will be summarized at week 16 by treatment group and site.

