If an adverse event occurs, the (sub)investigator will record the adverse event term,* date of onset, severity, seriousness, causal relationship to study drug, action taken with respect to study drug, non-study-drug-related actions, outcome, and the date of the outcome in the adverse event column of the case report form.

*: The adverse event terms will conform to the following criteria.

- As a rule, the diagnosis term will be used.
- If the diagnosis term is unclear, the symptom name will be used.
- If multiple symptoms emerge, if they indicate a single diagnosis term, then this diagnosis term will be used.
- Surgical procedures, etc. will not be considered adverse events; if an illness and/or symptom requiring a surgical procedure, etc. is confirmed, then this will be considered an adverse event.

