12.1 Study Drug Administration Discontinuation Criteria

If any of the following discontinuation criteria are met, the study drug administration will be discontinued.

- (1) If the subject asks to be discontinued from the study
- (2) If it is discovered that the subject is clearly unsuitable for study participation
- (3) If the (sub)investigator determines that it would be difficult to continue the study because of the emergence of, for example, an adverse event
- (4) If the (sub)investigator determines that it would not be appropriate to continue the study because of a worsening of the subject's underlying disease
- (5) If it becomes necessary to continue to administer one of the prohibited concomitant drugs or one of the prohibited concomitant therapies listed in "8.5.1 Prohibited Concomitant Drugs/Therapies"
- (6) If a joint replacement procedure is performed
- (7) If a clinically significant adverse event, as defined below, occurs.

- 1) Adjudicated arthropathy
- 2) Sympathetic nervous system disorder
- (8) If carpal tunnel syndrome is newly discovered, or if a worsening of symptoms pointing to carpal tunnel syndrome is observed
- (9) If it is discovered that the subject is pregnant
- (10) If the (sub)investigator determines that the study should be discontinued for some other reason.

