For subjects for whom the observations/tests stipulated at discontinuation could not be performed or who failed to come in for visits following discontinuation, follow-up investigations will be performed by written correspondence, telephone calls, etc. to determine the reasons why as well as the subsequent courses, etc. of the subjects.

The (sub)investigator or a study support staff member will to the extent possible recover the treatment diaries of subjects who failed to come in for site visits.

*As the "reason for discontinuation," one of the following reasons will be selected.

1. Adverse event
2. Death
3. Worsening of underlying disease
4. Insufficient efficacy
5. Unable to continue the study (the study cannot be continued because, for example, the subject moved due to personal circumstances)
6. The subject is clearly unsuitable for study participation
7. The subject dropped out of the observation period
8. The (sub)investigator determined that the study should be discontinued
9. Deviation from study protocol
10. Pregnancy
11. Technical problem
12. Request from the subject for discontinuation
13. Discontinuation of the study at the study site by the study sponsor
14. Discontinuation of the entire study by the study sponsor
15. Other reason

13. Statistical Analysis

This chapter will only include that information about the method of statistical analysis that is needed to achieve the primary objectives of this study; a more detailed, technical explanation of the statistical analysis methodology will be included in the statistical analysis plan (SAP), which is being prepared separately.

In this study, For the data obtained from screening to Week 16, from screening to Week 24 and from screening to post-treatment observation period of Week 20 after the end of the treatment period, a statistical analysis will be respectively performed. Statistical analysis plans will be prepared for each of these analyses, and these statistical analysis plans will be finalized before each data lock (data lock will be performed 3 times).

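### The return-to-baseline imputation names only lack of efficacy and AEs, so stops coded as worsening of the underlying disease escape the shift and joint-replacement stops depend on the code chosen

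*SAP*

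**What the plan says.** The Week 16 SAP, section 8.2.1, describes a multiple-imputation analysis that sorts patients by why they stopped. For one group, missing scores are placed around the average baseline of the randomized arm: "The missing data for patients who discontinued treatment due to lack of efficacy or AEs will be imputed with values centered". For everyone else, "The missing data for patients discontinued treatment due to other reasons will be imputed under missing-at-random assumption", by regression on treatment, strata and baseline. Step 1 explains MAR: "the missing data are assumed to follow the same model as the other patients in their respective treatment group". Step 2 adds the patient's own earlier visit scores as predictors. Step 3 applies the return to baseline, again only for lack of efficacy or AEs, by subtracting the arm's mean on-treatment change from the MAR-imputed score.

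The reasons come from Protocol 12.3, where the site selects one item from a list of 15. Adverse event is item 1. Two further items are "3. Worsening of underlying disease" and "4. Insufficient efficacy". Protocol 12.1 makes the same separation among the criteria for stopping study drug: item (3) concerns adverse events, and item (4) applies when the investigator judges that it "would not be appropriate to continue the study because of a worsening of the" underlying disease.

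Item (6) of 12.1 stops study drug "If a joint replacement procedure is performed". No item in the 12.3 list corresponds to it. Protocol 9.2.4.2 says "Surgical procedures, etc. will not be considered adverse events", but the same sentence goes on to make the illness or symptom that requires surgery an adverse event.

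No readable SAP text maps the 12.3 codes to the two imputation groups.

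**The concern.** The underlying disease is osteoarthritis and the endpoint is osteoarthritis pain. A patient withdrawn because the disease worsened has had a poor outcome on the endpoint, close in meaning to insufficient efficacy. The analysis exists to remove assumed benefit from patients who stopped for bad outcomes, yet its wording leaves this reason in the group that keeps the MAR value.

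The codes also overlap. Protocol 9.2.4.2 counts a clinically significant worsening of existing symptoms, temporally related to study drug, as an adverse event. A flare of joint pain that ends treatment could therefore be recorded as code 1, 3 or 4, and only code 3 avoids the shift. The sensitivity result then depends partly on coding habit.

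For joint replacement the problem is ambiguity. The allocation is undefined, and the post-replacement schedule (Protocol 9.1.1 (3)) contains no WOMAC, so a patient operated on before Week 16 will probably have no Week 16 score.

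**Working it through.** **Inputs**
- LS mean change in WOMAC pain at Week 16 in the earlier phase 2/3 study: −3.35 on 1 mg, −2.25 on placebo (SAP Table 3.3-1).
- Design difference 1.1, SD 2.5, 120 completers per arm, 15% missing at Week 16 (SAP 3.3).
- Shares of patients with a reclassified missing score, f_drug and f_placebo: not in the documents, so assumed.

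**Plan's own figures.** −3.35 − (−2.25) = −1.10, which matches the tabulated difference. 120/0.85 = 141.2, rounded up to 142, which matches the stated group size. The imputation rule itself carries no stated figure.

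**Effect of reclassifying one patient.** Step 3 sets the final score to the MAR score minus the arm's mean change. The mean change is negative, so the score rises by its absolute value: about 3.35 on 1 mg and 2.25 on placebo. This holds whatever the MAR score was, apart from truncation to the 0–10 range.

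**Effect on the Week 16 difference.** Change = 3.35·f_drug − 2.25·f_placebo. A positive value means a smaller apparent benefit after reclassification.

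| f_drug | f_placebo | Change | Difference, from −1.10 |
|---|---|---|---|
| 3% | 3% | 0.1005 − 0.0675 = 0.033 | −1.067 |
| 5% | 2% | 0.1675 − 0.0450 = 0.1225 | −0.978 |
| 2% | 5% | 0.0670 − 0.1125 = −0.0455 | −1.146 |
| 15% | 15% | 0.5025 − 0.3375 = 0.165 | −0.935 |

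The last row reclassifies every missing score in both arms at the planned rate, so it is the ceiling for equal shares.

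**Direction.** The change is zero when f_drug/f_placebo = 2.25/3.35 = 0.67. Above that ratio, which includes equal shares, the rule as written flatters the drug. Below it, the rule is conservative.

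**Scale.** 0.1225/1.1 = 11% of the design difference. With 120 per arm the standard error is 2.5 × √(2/120) = 0.323, so 0.1225 is about 0.4 of a standard error.

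**Choice of mean.** The arithmetic means in the same table (−3.49 and −2.43) give 0.032, 0.126 and −0.052 for the first three rows, so the choice hardly matters.

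**The case against.** The strongest reply is that the SAP's lack of efficacy may be a concept that already includes worsening, since the phrase is not a verbatim 12.3 code. Subject-handling rules are left to sponsor decisions before lock (Protocol 13.1) and to separate data-review material (SAP section 5), and the SAS code is blacked out. A mapping could exist there. This is fair, but the visible text gives none, and the code blocks are introduced as imputation and pooling steps.

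Other objections stand and limit the point:

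- A reader might infer that these patients are credited with full benefit. Step 2 uses their own earlier scores, so someone already worsening is imputed worse than the arm mean. What is missing is the return-to-baseline shift.
- A reader might infer that joint-replacement stops are always imputed under MAR. The documents do not say so: the condition leading to surgery is an AE, and adjudicated arthropathy is itself listed as an adverse event in 12.1 (7).
- A reader might add stops for needing a prohibited treatment, 12.1 (5). The list in Protocol 8.5.1 includes immunosuppressants and biologics, so these are not all pain failures.
- Some scores may not be missing. WOMAC is due at treatment discontinuation, and follow-up after the last dose would supply a Week 16 score after a last dose at Week 0, 8 or 12. The SAP does not say whether scores after stopping are used.
- The tipping-point analysis is not stated to be limited by reason and partly covers the gap. It asks how large a shift overturns the result, so it does not settle how this reason-based analysis should classify stops.

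**Conclusion.** The point holds in this form: followed as written, code 3 stops are left out of the return to baseline, and joint-replacement stops have no defined place. Within the assumed scenarios of 2% to 5% per arm, the Week 16 difference moves by −0.05 to 0.12. This rests on prior-study LS means standing in for the trial's own on-treatment means, on 1 mg q8w behaving like the tabulated 1 mg arm (the plan assumes 1.1 for both), on little truncation, and on assumed shares.

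A reader might infer a bias in favour of the drug. The documents do not support that, because they give no split of stops by reason or arm, and more such stops on placebo would reverse the sign. Only one sensitivity analysis is affected; the primary MMRM and the multiplicity procedure are not. It is worth correcting because the classification bears directly on outcome and is currently left to interpretation.

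**What to change.** In section 8.2.1 of the Week 16 SAP, before unblinding, define the return-to-baseline group by the Protocol 12.3 codes: 1 (adverse event), 3 (worsening of underlying disease) and 4 (insufficient efficacy). Assign missing Week 16 scores after a joint replacement to the same group whatever code was ticked. Leave the remaining reasons under MAR, and repeat the definition in Step 3.

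The cost is a sentence or two of SAP text and a changed flag in the imputation program. The reason code is already collected; joint replacements without an AE, worsening or efficacy code must be identified from the other trial records. The estimate may become less favourable if such stops are commoner on active drug. A sponsor who prefers another mapping should still write it down before unblinding.
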